4.2.2.1. Adverse Events

An AE is any untoward medical occurrence that may present during treatment with a pharmaceutical product, but which does not necessarily have a causal relationship with this treatment (WHO 2012²⁵).

A treatment-emergent AE (TEAE) will be defined as any new AE reported or any worsening of an existing condition on or after the first dose of BDQ drug, and up to and including 30 days after last BDQ dose.

Seriousness of AE will be graded per the following (WHO 2012²⁵):

-
- Not serious
 - Results in hospitalization (caused or prolonged)
 - Results in permanent disability
 - Results in congenital abnormality
 - Is life-threatening
 - Results in death

Serious AEs are those AEs that are graded in any seriousness category other than the “Not Serious” category.

Relation of AEs (e.g., whether there is a reasonable possibility that the study drug caused the event) using the following requirements (WHO 2012²⁵):

- Probable: the event is an identifiable clinical or laboratory phenomenon; the time elapsed between the administration of the drug and the occurrence of the event is plausible; the event cannot be explained by concurrent disease or any other drug or chemical; the patient recovered within a plausible length of time following withdrawal of the drug; rechallenge did not occur, or the result is unknown.
- Possible: the time elapsed between the administration of the drug and the occurrence of the event is plausible; the outcome of withdrawal of the suspect medicine is not known, and/or the medicine might have been continued and the final outcome is not known; and/or there might be no information on withdrawal of the medicine; and/or the event could be explained by concomitant disease or use of other drugs or chemicals; and/or there might be no information on the presence or absence of other medicines.
- Unrelated (Unlikely): the event occurred with a duration to onset that makes a causal effect improbable with the drug being considered and/or; the event commenced before the first administration of the drug; and/or the drug was withdrawn and this made no difference to the event when, clinically, recovery would be expected; and/or it is strongly suggestive of a non-causal relationship if the drug was continued and the event resolved.

The following will be used for grading the severity of AEs following WHO (WHO 2012²⁵):

- Mild

-
- Moderate
 - Severe

Severity does not have the same meaning as seriousness. The degree of severity reflects the intensity of the event. A patient can experience a severe event that is not serious, e.g. pruritus.

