2. OVERVIEW OF STUDY DESIGN

2.1. Study Design

The research design uses a prospective observational comparative cohort study of patients treated for MDR-TB in multiple countries included in the early adopter (WHO pilot) program. A case of tuberculosis is one in which a health worker (clinician or other medical practitioner) has diagnosed TB. MDR-TB is defined as TB caused by *Mycobacterium tuberculosis* resistant in vitro to the effects of isoniazid and rifampicin, with or without resistance to any other drugs. Patients are enrolled in the registry by their healthcare provider once the healthcare provider diagnoses a patient with MDR-TB (inception cohort for comparison) or decides to treat with BDQ (exposure cohort specifically identifying indication for use for BDQ). All patient follow-up data will be collected at each visit from the healthcare provider during the course of BDQ treatment and for an additional 24 months after the last BDQ dose unless the patient is lost to follow-up or has died. Similar follow-up will be conducted for MDR-TB patients not treated with BDQ. Two options are under evaluation for the recruitment of MDR-TB patients not treated with BDQ. The first option under consideration is to include patients who are eligible for BDQ, but refuse BDQ at sites where BDQ is available. The second

option under consideration is the use of a stepwise cluster wedge design to enroll patients at centers who would be eligible for BDQ, but do not have access. The method for selecting MDR-TB patients not treated with BDQ will depend on how BDQ is made available in the early adopter countries. All patients newly diagnosed and treated for MDR-TB will be eligible for inclusion in the registry. Additionally, all patients initiating BDQ treatment will be eligible for inclusion in the registry regardless of the indication for use. All patients meeting the inclusion criteria and providing informed consent for participation in the study will be enrolled. The registry enrollment period will be open for 36 months with an additional 24 months of follow-up for safety assessment. This enrollment period should allow the enrollment of approximately 3000 MDR-TB patients treated with BDQ.

Data will be collected in an observational manner such that the management of the patient is determined by the patient and the caregiver and not influenced by the registry protocol. The registry will describe care as it is provided.

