4.2.2. Outcome Definitions and Measures

The registry is designed to observe several aspects of MDR-TB treatment such as drug utilization characteristics, treatment outcomes (clinical and microbiologic), and safety outcomes (adverse events and mortality). All study outcomes will be documented by the healthcare provider and will be reported up to 24 months after discontinuation of MDR-TB treatment.

Study outcome definitions will include:

- Medical indication for BDQ treatment as reported by the healthcare provider
- Frequency of use of expert medical consultation in MDR-TB treatment with BDQ
- Drug susceptibility of MDR-TB isolates (Pre-XDR, XDR) and drug susceptibility to BDQ based on MIC reported

-
- Laboratory location and type performing susceptibility testing as well as type of test performed
 - Past treatment history, past medical history, prior medications utilization, and health care site of treatment
 - Use of DOT for drug administration
 - Adverse events including deaths over the course of MDR-TB therapy recorded using WHO guidance for pharmacovigilance of medicines used in the treatment of tuberculosis (WHO 2012²⁵)
 - Comorbidities prior to initiating MDR-TB therapy as well as over the course of therapy
 - Concomitant medications prior to initiating MDR-TB therapy as well as over the course of therapy
 - Reason for discontinuation of MDR-TB therapy
 - Change in TB background regimen (Y/N)
 - Cavities on chest x-ray
 - Acid fast bacilli-smear $\geq 1+$ (Y/N)

The following definitions will be used for treatment outcomes among MDR-TB cases (WHO, 2013³⁰):

- Cured: Treatment completed as recommended by the national policy without evidence of failure AND three or more consecutive cultures taken at least 30 days apart are negative after the intensive phase^a.
- Treatment Completed: Treatment completed as recommended by the national policy without evidence of failure BUT no record that three or more consecutive cultures taken at least 30 days apart are negative after the intensive phase^a.
- Treatment Failed: Treatment terminated or need for permanent regimen change of at least two anti-TB drugs because of:
 - Lack of conversion^b by the end of the intensive phase^a, *or*
 - Bacteriological reversion^b in the continuation phase after conversion^b to negative, *or*

-
- Evidence of additional acquired resistance to fluoroquinolones or second-line injectable drugs, *or*
 - Adverse drug reactions (ADRs).

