4.2.4. Length of Follow-up

Each patient will be followed for 24 months from the discontinuation of MDR-TB therapy, until death, or loss to follow-up within the cohort, whichever occurs first. Time varying variables will be recorded at each patient visit.

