4.3.2. Specific Comparisons

The observed rates of adverse events and death among BDQ-treated patients will be compared with the observed rates of adverse events and death among patients with similar clinical characteristics, but not treated with BDQ.

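### Follow-up ends 24 months after the last BDQ dose in some sections and 24 months after MDR-TB therapy in others, so the BDQ versus no-BDQ safety comparison has no single observation window

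*Protocol*

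**What the plan says.** Two ends of follow-up stand in the current Protocol.

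- **BDQ anchor.** Section 2.1 collects follow-up data "during the course of BDQ treatment and for an additional 24 months after the last BDQ dose", and the synopsis says the same. For the comparison cohort it adds only: "Similar follow-up will be conducted for MDR-TB patients not treated with BDQ".
- **Therapy anchor.** Section 4.2.2 has all study outcomes "reported up to 24 months after discontinuation of MDR-TB treatment". Section 4.2.4 states: "Each patient will be followed for 24 months from the discontinuation of MDR-TB therapy".

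Section 4.2.2.1 defines a treatment-emergent adverse event as one arising or worsening "on or after the first dose of BDQ drug, and up to and including 30 days after last BDQ dose". No counterpart is given for patients without BDQ.

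The comparison that needs these windows is a primary objective (section 1.3.1). Section 4.3.2 repeats it: "The observed rates of adverse events and death among BDQ-treated patients will be compared with the observed rates" in similar patients not given BDQ. Section 4.4.2.2 divides event counts by exposure person-time, without saying whether that is time on BDQ or time on the regimen, and plans Poisson regression. Section 4.4.2.1 also promises proportions with 95% confidence intervals by cohort for each objective.

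**The concern.** A cohort comparison of adverse events and deaths needs a start and a stop that can be applied to both groups. Here one of the two stops, and the whole treatment-emergent window, depend on BDQ doses that comparators never receive. Section 4.2.1 records start and stop dates drug by drug, so the protocol itself allows BDQ to stop on a different day from the rest of the regimen.

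This is more than a matter for the analysis plan. How long a site follows a patient is a data-collection rule. A site that reads section 2.1 literally could close a BDQ patient's record before a site following section 4.2.4 would. Deaths and adverse events after that point would not be collected, and no later analysis could recover them.

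**Working it through.** No figure in the Protocol depends on the follow-up window. The 3% event frequency in section 4.1 has no period attached, so there is no stated result to reproduce. The check is date arithmetic followed by an illustration.

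**Inputs**
- Regimen length 24 months: sections 1.1.4 and 1.1.5 speak of up to, or on average, 2 years.
- BDQ course of d months, starting with the regimen: not stated, so an assumption, varied from 3 to 24.
- No true effect of BDQ on the event rate, and no losses.
- Mixed reading: section 2.1 applied to BDQ patients, section 4.2.4 to comparators.

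**Step 1: length of observation.** BDQ patients: d + 24 months. Comparators: 24 + 24 = 48 months. For d = 6 this is 30 against 48, a gap of 18 months.

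**Step 2: person-time rates.** Let the on-therapy rate be 1 and the post-therapy rate r. The average rate is (24 + r·d)/(d + 24) in BDQ patients and (24 + 24r)/48 in comparators. For d = 6:
- r = 1: 30/30 = 1 against 48/48 = 1, ratio 1.00.
- r = 0.5: 27/30 = 0.90 against 36/48 = 0.75, ratio 1.20.
- r = 0.25: 25.5/30 = 0.85 against 30/48 = 0.625, ratio 1.36.

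**Step 3: simple proportions.** Take a 3% risk over 24 months at a constant rate (the period is an assumption). Then λ = −ln(0.97)/24 = 0.00127 per month, and the risk over w months is 1 − exp(−λw). For d = 6: 3.74% at 30 months against 5.91% at 48, ratio 0.63.

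| Assumed BDQ course (months) | Follow-up, BDQ vs comparator (months) | Rate ratio, r = 1 | r = 0.5 | r = 0.25 | Ratio of proportions |
|---|---|---|---|---|---|
| 3 | 27 vs 48 | 1.00 | 1.26 | 1.47 | 0.57 |
| 6 | 30 vs 48 | 1.00 | 1.20 | 1.36 | 0.63 |
| 12 | 36 vs 48 | 1.00 | 1.11 | 1.20 | 0.76 |
| 18 | 42 vs 48 | 1.00 | 1.05 | 1.09 | 0.88 |
| 24 | 48 vs 48 | 1.00 | 1.00 | 1.00 | 1.00 |

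Every entry should be 1.00. The two measures err in opposite directions.

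**Step 4: registry closure.** Section 2.1 gives 36 months of enrollment plus 24 of follow-up. If the registry closes at month 60 and enrollment is uniform, available follow-up runs evenly from 24 to 60 months. For d = 6, mean follow-up is (6/36)·27 + (30/36)·30 = 29.5 months in BDQ patients and (24/36)·36 + (12/36)·48 = 40 months in comparators. The rate ratios become:
- r = 0.5: (26.75/29.5)/(32/40) = 1.13.
- r = 0.25: (25.375/29.5)/(28/40) = 1.23.

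Closure shrinks the distortion but does not remove it.

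**The case against.** The strongest reply is that section 4.2.4 is the section on length of follow-up, covers each patient and so treats both cohorts alike, while section 2.1 promises comparators similar follow-up. No sentence assigns different ends to the two cohorts, and unequal windows arise only by mixing sections. That is right: unequal observation is possible, not prescribed. But nothing gives section 4.2.4 precedence over the study design section, and the synopsis sides with section 2.1.

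A second reply is that the planned measure is a person-time rate, which unequal windows do not bias under a constant event rate. This also stands, as the r = 1 column shows. It does not cover a changing rate, the proportions promised in section 4.4.2.1, or a denominator whose exposure is undefined.

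Stronger readings that a reader might infer are not supported:
- *That the treatment-emergent definition biases the relative risk.* With a 6-month course, 7 months against 25 would suggest a null risk ratio near 0.28. But sections 1.3.1, 4.3.2 and 4.4.2.2 compare adverse events, not treatment-emergent ones, and no 25-month comparator window appears in the Protocol.
- *That mortality will be biased in favour of BDQ.* A ratio of 0.66 follows if the 15% mortality in section 1.1.5 is spread over 24 months and carried on at a constant rate. That figure has no stated period, and the result is a ratio of cumulative risks. The planned rate ratio would be 1.00 under the same constant rate and above 1 if mortality falls after therapy.
- *That section 4.2.2 contradicts itself on deaths.* Its bullet reads "Adverse events including deaths over the course of MDR-TB therapy recorded", but it sits under a lead sentence extending all outcomes to 24 months after treatment. The bullet could be clearer; it is not a separate conflict.

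**Conclusion.** The contradiction is real and in the current text: two incompatible ends of follow-up, a treatment-emergent window that exists for one cohort only, and an exposure denominator that is not tied to either anchor. The consequence is conditional. If sites or analysts apply the BDQ anchor to BDQ patients and the therapy anchor to comparators, BDQ patients could be observed for a shorter time and their later events lost.

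Neither size nor direction can be read from the Protocol. Both depend on BDQ duration, the measure used and how the event rate changes over time. Under the assumed 24-month regimen and 6-month BDQ course, the null rate ratio ranges from 1.00 (constant rate) through 1.20 to 1.36 (post-therapy rate a half or a quarter), or 1.13 and 1.23 with closure at month 60. Proportions fall below 1. All of this disappears if BDQ and the regimen end together. The point merits correction because it touches a primary comparative objective and because uncollected follow-up cannot be restored.

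**What to change.** 1. Reconcile the synopsis and section 2.1 with sections 4.2.2 and 4.2.4, so that follow-up in both cohorts ends at one anchor: 24 months after the end of the TB treatment regimen, or registry close. State an equivalent for BDQ users treated outside MDR-TB, whom section 2.1 enrolls whatever the indication and who may have no MDR-TB therapy end date.
2. Fix the registry closing date as well. Section 7.3.1 completes the study three years after registry start, which does not fit 36 months of enrollment plus 24 of follow-up.
3. For comparative analyses of adverse events and death, define person-time and the event window from dates that exist in both cohorts, and say in section 4.4.2.2 which exposure the denominator counts.
4. Choose a comparable time zero that handles BDQ added to an ongoing regimen, for example comparators matched on time since regimen start, or BDQ as a time-varying exposure. Using BDQ start in one cohort and regimen start in the other would put the cohorts on different clocks.
5. Keep the treatment-emergent window of section 4.2.2.1 for description within the BDQ cohort, and say so.

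The cost is mainly wording, since section 4.2.1 already collects start and stop dates for every drug. Some BDQ patients would be followed longer than section 2.1 implies (18 months longer in the 6-month illustration, before closure), but section 4.2.4 already requires this.

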4.2.3. Potential Confounders and Effect Modifiers

Potential confounders and effect modifiers will be collected and used to describe the cohort. Patient factors will include demographics, comorbidities and concomitant medications that might influence MDR-TB treatment use.

- Age
- Sex
- Weight or BMI
- Ethnicity
- Length of TB infection
- Evidence of cavitory disease on chest X-RAY
- Depression
- HIV/AIDS
- Diabetes
- Cardiovascular risk factors for QT prolongation, electrolyte abnormalities and arrhythmia (including medications)
- Hepatic risk factors (alcohol use, history of liver disease, chronic hepatitis)
- TB drug susceptibility to Isoniazid and rifampin, as well as pre-XDR/XDR
- Prior treatment with TB therapy
- Prior adherence to TB therapy
- Concomitant TB therapy administered with BDQ

-
- Substance use

4.2.4. Length of Follow-up

Each patient will be followed for 24 months from the discontinuation of MDR-TB therapy, until death, or loss to follow-up within the cohort, whichever occurs first. Time varying variables will be recorded at each patient visit.

4.3. Analyses

4.3.1. Descriptive Analysis

Frequencies, proportions, and rates will be determined as appropriate based on each study objective.

4.3.2. Specific Comparisons

The observed rates of adverse events and death among BDQ-treated patients will be compared with the observed rates of adverse events and death among patients with similar clinical characteristics, but not treated with BDQ.

4.4. Statistical Analysis Plan

4.4.1. Analysis of Baseline Characteristics

Baseline characteristics including demographics, country of origin, medical history, susceptibility of baseline MDR-TB isolates to BDQ and TB background regimen drugs, and use of medications at cohort entry will be described. The analysis will report the frequency distribution (number and percentage of patients) for categorical variables and descriptive statistics (median, mean, standard deviation [SD]) for continuous variables.

4.4.2. Analysis of Study Objectives

4.4.2.1. Descriptive Analyses

This analysis will describe and summarize the prescribing and utilization of MDR-TB treatments, as well as patient treatment outcomes (clinical and microbiologic), and TB isolate susceptibility. MDR-TB treatment will be summarized by patient demographics and clinical characteristics (comorbidities and concomitant medications). In addition, the details of MDR-TB treatment will be described including indication of use, dose, frequency, duration of use, usage with TB background regimen, and susceptibility of concomitant TB treatment regimens. Patients treated with BDQ outside of the MDR-TB indication will be summarized by patient demographics and clinical characteristics including indications of use, frequency, duration of use, usage with TB background regimen, and susceptibility of concomitant TB treatment regimens. Additionally,

treatment outcomes will be described separately for MDR-TB cases and non MDR cases or MDR status not documented (WHO, 2013³⁰).

Proportions and 95% confidence intervals will be estimated separately for BDQ-treated patients and non-BDQ-treated patients for each study objective.

Additionally the following treatment outcomes will be estimated separately for patients with MDR-TB for BDQ-treated patients and non-BDQ-treated patients: cured, treatment completed, treatment failed, died, lost to follow-up, not evaluated, and treatment success.

Analyses of MDR-TB drug susceptibility will use the total number of MDR-TB patients included in the registry. Proportions will describe the number of subjects whose post-enrollment isolates exhibit at least 4-fold increase in BDQ MIC in comparison to baseline MIC, provided that the post-baseline MIC is >0.25 mg/mL based on phenotypic methods on solid or liquid media. Additional proportions will describe the number of patients with pre-XDR and XDR-TB.

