1.3. STUDY OBJECTIVES

1.3.1. Primary Objectives:

The following primary objectives were specifically chosen to address gaps in the currently available data informing BDQ benefits and risks:

- To describe the type of hospital or outpatient setting administering MDR-TB treatment
- To describe MDR-TB treatment delivery modalities, including treatment and management programs in place, administration of drug under closely monitored conditions, and consultation with experts in clinical management of MDR-TB and public health authorities such as national MDR-TB advisory groups within National TB Control Programs
- To describe the demographic and clinical characteristics of MDR-TB patients participating in the registry
- To describe MDR-TB treatment regimen utilization including dosages, duration, past treatment history, past medical history, concomitant medications used for conditions other than TB
- To measure adherence to WHO guidance in terms of selection of MDR-TB regimens and selection of patients for BDQ treatment

- To describe the indication for use of BDQ
- To measure extent to which patient informed consent is obtained for receipt of BDQ
- To describe BDQ and background drug susceptibility testing expressed as minimum inhibitory concentration (MIC) at baseline and for isolates from the last positive specimens
- To actively monitor adverse events using cohort event monitoring, including the monitoring for drug-drug interactions
- To actively monitor for mortality events using cohort event monitoring that includes collection of cause of death where available
- To estimate the relative risk of adverse events and mortality events by comparing event rates among BDQ-treated patients to respective event rates among patients not treated with BDQ, adjusting for potential imbalances in predictors of receiving BDQ for treatment, as well as predictors of mortality, assuming the availability of comparable populations
- To describe the following treatment outcomes separately for patients with MDR-TB and patients with non- MDR cases or MDR status not documented, as stipulated by the WHO revised definitions for resistant TB cases in 2013: cured, treatment completed, treatment failed, died, lost to follow-up, not evaluated, and treatment success
- To compare the treatment outcomes of cured, treatment completed, treatment failed, died, lost to follow-up, not evaluated, and treatment success between BDQ-treated patients and patients not treated with BDQ

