- Died: A patient who dies for any reason during the course of treatment.
 - Lost to Follow-Up: A patient whose treatment was interrupted for 2 consecutive months or more.
 - Not Evaluated: A patient for whom no treatment outcome is assigned. (This includes cases “transferred out” to another treatment unit and whose treatment outcome is unknown)
 - Treatment Success: The sum of cured and treatment completed

^a For *Treatment failed*, lack of conversion by the end of the intensive phase implies that the patient does not convert within the maximum duration of intensive phase applied by the program. If no maximum duration is defined, an 8-month cut-off is proposed. For regimens without a clear distinction between intensive and continuation phases, a cut-off 8 months after the start of treatment is suggested to determine when the criteria for *Cured*, *Treatment completed* and *Treatment failed* start to apply.

^b The terms “conversion” and “reversion” of culture as used here are defined as follows:

Conversion (to negative): culture is considered to have converted to negative when two consecutive cultures, taken at least 30 days apart, are found to be negative. In such a case, the specimen collection date of the first negative culture is used as the date of conversion.

Reversion (to positive): culture is considered to have reverted to positive when, after an initial conversion, two consecutive cultures, taken at least 30 days apart, are found to be positive. For the purpose of defining *Treatment failed*, reversion is considered only when it occurs in the continuation phase.

The following definitions will be used for treatment outcomes among non MDR cases or MDR status not documented (WHO 2013³⁰):

- Cured: A pulmonary TB patient with bacteriologically confirmed TB at the beginning of treatment who was smear- or culture-negative in the last month of treatment and on at least one previous occasion.
- Treatment Completed: A TB patient who completed treatment without evidence of failure BUT with no record to show that sputum smear or culture results in the last month of treatment and on at least one previous occasion were negative, either because tests were not done or because results are unavailable.

-
- Treatment Failed: A TB patient whose sputum smear or culture is positive at month 5 or later during treatment.
 - Died: A TB patient who dies for any reason before starting or during the course of treatment.

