4.5. Evaluation of Appropriateness of Comparison Study

The evaluation of appropriateness of a comparison of BDQ-exposed patients with non-BDQ-treated MDR-TB patients will be based on the consistency of the clinical

experience of the 2 cohorts. This assessment will be conducted based on distribution of propensity scores for receipt of BDQ or other treatment regimens.

The evaluation of clinical experience will assess the patients' clinical and demographic characteristics in relation to receipt of BDQ and other MDR-TB regimens. Information will be captured on the patients' clinical and demographic characteristics that could be predictive of treatment appropriateness. This information will be incorporated into multivariate model to identify a group of patients with similar characteristics to the BDQ cohort but treated with other MDR-TB treatments. All patients will be assigned a propensity score ranging from 0 to 1 that represents the fitted probability of receiving BDQ. The scores from non-BDQ-treated patients will be plotted against those for BDQ-treated patients. Overlap in the cohorts based on sample size estimates of approximately 750 patients per treatment group in the propensity space must exist for a comparison of safety events between the two groups. An epidemiologist trained in propensity score estimation and matching methodology will make this assessment on the epidemiological validity of a comparison between the 2 treatment cohorts.

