A standard query follow-up regimen of four attempts is used at two-week intervals using phone, fax, mail and/or e-mail as appropriate for query resolution. If no further information is obtained on an otherwise evaluable case, the discrepant data fields may be left blank or identified as “Unknown” as appropriate. However, some cases may be flagged as “Lost to Follow-Up” or “Not Valid” if critical data required to evaluate the case is missing or unknown.

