5. STUDY LIMITATIONS

The proposed study is based on analysis of prospective cohort data provided by healthcare providers treating patients with BDQ. The following limitations should be considered:

The registry may include bias related to the observational nature of the data and potential lack of data due to loss to follow-up or essential data not collected as routine fields.

These studies are also subject to real-world prescribing practices that may not provide sufficient patient numbers to meet study goals of ascertainment within a reasonable timeframe. Additionally, participation in the registry may influence prescribing of BDQ in routine patient care.

Allocation of treatment is not subject to randomization. Patients will likely be channeled to treatment based on several measured and unmeasured characteristics and based on treatment guidelines. This potentially introduces associations between exposures and outcomes that are confounded.

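### The primary comparison of treatment outcomes has only separate proportions by arm as its stated analysis, while adjustment and the overlap condition are worded for safety events, so it is open to confounding by indication

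*Protocol*

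**What the plan says.** Section 1.3.1 lists two separate primary objectives on treatment outcomes. One is to describe them. The other is "To compare the treatment outcomes of cured, treatment completed, treatment failed, died, lost to follow-up, not evaluated, and treatment success between BDQ-treated patients" and those not treated with BDQ. This second objective mentions no adjustment and sets no condition on comparability.

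The objective on adverse events and mortality, in the same list, carries both: "adjusting for potential imbalances in predictors of receiving BDQ for treatment, as well as predictors of mortality, assuming the availability of comparable populations".

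The analysis sections follow the same split:

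- Section 4.3.2, on specific comparisons, covers safety only: "The observed rates of adverse events and death among BDQ-treated patients will be compared with the observed rates of adverse events and death among patients" who are clinically similar but untreated with BDQ.
- Section 4.4.2.1 is headed as descriptive. It says "Proportions and 95% confidence intervals will be estimated separately for BDQ-treated patients and non-BDQ-treated patients for each study objective", and then lists the treatment outcomes to be estimated separately by arm among MDR-TB patients.
- Section 4.4.2.2, on adverse events, holds the Poisson regression, the adjustment for imbalance and the optional propensity methods. It includes death, and it fixes the adjustment method in advance for comparisons of safety outcomes.
- Section 4.5 says that overlap of about 750 patients per group in the propensity space "must exist for a comparison of safety events between the two groups".

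Section 5 warns: "Patients will likely be channeled to treatment based on several measured and unmeasured characteristics". The Synopsis adds that BDQ is indicated where no other effective regimen can be provided.

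**The concern.** An objective to compare needs an analysis that can support a comparison. Two proportions with their own intervals, set next to each other, invite the reader to take the gap as an effect of BDQ. If BDQ goes mainly to patients with few remaining options, part or all of that gap reflects who was chosen for the drug.

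The protocol sees this risk and deals with it for safety. Its wording does not carry the remedy over to cure, completion, failure and success. Read literally, the two cohorts could fall short of the overlap condition for adverse events and still be set against each other on cure. These outcomes are the effectiveness side of a registry intended to inform benefit and risk, so a misleading gap in either direction would matter.

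**Working it through.** **1. The plan's own figures.** The protocol gives no precision or power figure for treatment outcomes. Its sizing (4.1) is for adverse events: 1000 per group, 3% against 6% (relative risk 2), alpha 0.05, power 95% (0.954 in the table). The usual two-proportion formula is

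power = Φ{ [|p2 − p1| − z·√(2p̄(1 − p̄)/n)] / √[(p1(1 − p1) + p2(1 − p2))/n] }.

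With n = 1000 it gives 0.945 one-sided, close to the stated value, and 0.900 two-sided. With n = 750 it gives 0.801 two-sided. The threshold of about 750 in 4.5 is therefore consistent with safety-event sizing. The point below does not depend on these figures.

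**2. Coverage of each comparison, as the text stands.**

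| | Adverse events and death | Cure, completion, failure, success |
|---|---|---|
| Comparison is a primary objective (1.3.1) | yes | yes |
| Adjustment named in the objective | yes | no |
| Listed in specific comparisons (4.3.2) | yes | no |
| Model or propensity method (4.4.2.2) | yes | no |
| Overlap threshold (4.5) | yes (safety events) | not named |
| Stated analysis | adjusted relative risks | proportions by arm (4.4.2.1) |

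**3. How large a spurious gap could be.** Suppose one binary severity factor and no BDQ effect. Let success be s1 in severe and s0 in other patients, and let the severe share be a in comparators and b in BDQ patients. Crude success in an arm is share × s1 + (1 − share) × s0, so the spurious difference is

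(b − a) × (s1 − s0).

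Inputs: 9.6% and 13.7% are the global and the EU/EEA shares of XDR-TB among MDR-TB in section 1.1.1, used here only as plausible severe shares. All other shares and all success rates are assumptions. For scale, section 1.1.5 cites 48% success overall in the 2010 cohort.

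| s0 / s1 | a → b | Crude success, comparators vs BDQ | Spurious difference |
|---|---|---|---|
| 50% / 40% | 9.6% → 13.7% | 49.0% vs 48.6% | −0.4 points |
| 50% / 40% | 9.6% → 30% | 49.0% vs 47.0% | −2.0 |
| 50% / 40% | 9.6% → 50% | 49.0% vs 45.0% | −4.0 |
| 55% / 30% | 9.6% → 13.7% | 52.6% vs 51.6% | −1.0 |
| 55% / 30% | 9.6% → 30% | 52.6% vs 47.5% | −5.1 |
| 55% / 30% | 9.6% → 50% | 52.6% vs 42.5% | −10.1 |
| 52% / 30% | 20% → 50% | 47.6% vs 41.0% | −6.6 (ratio 0.86) |
| 52% / 30% | 10% → 60% | 49.8% vs 38.8% | −11.0 (ratio 0.78) |

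The last row in full: 0.6 × 0.30 + 0.4 × 0.52 = 0.388; 0.1 × 0.30 + 0.9 × 0.52 = 0.498; difference −0.110.

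The sign is part of the assumption. If the severe patients were concentrated among comparators, every difference would reverse.

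**4. Would such a gap look convincing?** With 750 per group and a two-sided 5% test, the formula in step 1 gives the chance of rejecting in the direction of the bias, which would be 2.5% with no bias. It is about 4% for a gap of 0.4 points, 6% for 1.0, 12% for 2.0, 35% for 4.0, 51% for 5.1 and 98% for 10.1. The protocol specifies no such test. The figures only show how easily a gap of this size would pass for an effect.

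**The case against.** The strongest reply is that 4.4.2.1 is headed as descriptive, and proportions by arm with intervals are ordinary description. No crude difference, ratio or test is specified, and the Synopsis announces a separate statistical analysis plan that could supply an adjusted comparison. It is true that no crude contrast is spelled out. The point survives because it does not rest on missing detail. The protocol separates comparing from describing, gives the same by-arm analysis for every objective, and words its adjustment and overlap threshold for safety.

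Section 4.5 also opens and closes by speaking of a comparison of the two cohorts in general. A reader could fairly take it to govern any comparison, so the text does not establish that outcomes would be compared even after the cohorts were judged non-comparable. Its one operative threshold, however, names safety events.

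The comparator options in 2.1 (patients eligible for BDQ who refuse it, or eligible patients at centers without access) aim at BDQ-eligible controls, which would limit confounding by indication. Both were still under evaluation, and section 5 expects channeling regardless. This is a good reason not to assume that the larger imbalances in the table will occur.

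A reader might infer two stronger things. One is that death is also left unadjusted. It is not: 1.3.1, 4.3.2 and 4.4.2.2 all cover it, and only the WHO outcome category for death is tabulated by arm alone. The other is that section 4.6, which allows a lost-to-follow-up flag "if critical data required to evaluate the case is missing or unknown", would inflate the treatment outcome of the same name. That outcome is defined separately in 4.2.2, and 4.6 describes query resolution without saying that the flag feeds the outcome.

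**Conclusion.** The point holds for cure, completion, failure and treatment success. Comparing them is a primary objective, the only stated analysis is separate proportions, and the protocol's own safeguards against confounding are worded for safety events including death. The comparison as written is open to confounding by indication. The documents do not support saying that it is confounded by a known amount or in a known direction.

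Under no drug effect and one assumed severity factor, the spurious difference in success runs from under 1 to about 11 percentage points. The range rests on assumed success rates and largely assumed imbalances, and the upper end needs a severe share of 60% against 10%. This should be corrected in the protocol and not left to the analysis plan, because the restriction to safety is stated in the protocol itself.

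**What to change.** In 4.4.2.1, state that any between-cohort comparison of treatment outcomes uses the same a priori adjustment as 4.4.2.2, for example adjusted risk ratios and risk differences with 95% confidence intervals, in the population where the propensity scores overlap.

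In 4.5, extend the overlap condition from safety events to this comparison. If it is not met, report each arm descriptively and draw no comparative conclusion. The by-arm proportions can stay as description in either case.

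The cost is a few sentences, a little more analysis work and somewhat wider intervals. The covariates (4.2.3) and the propensity model (4.5) are already planned, and no sample size changes. Adjustment deals only with measured factors, so the warning in section 5 about unmeasured channeling should accompany the results.
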